6. STUDY PROCEDURES AND ASSESSMENTS

The schedule of assessments is summarized in **Table 1**

6.1 Informed Consent

Enrollment in the study requires that all inclusion and exclusion criteria have been met. A patient may be enrolled into the study when the written informed consent has been obtained and the patient's eligibility per all inclusion and exclusion criteria has been confirmed.

6.2 Randomization

Randomization will occur using the GraphPad QuickCalcs randomization service.

6.3 Study Visits

Patients will be evaluated at scheduled visits over the following study periods: Screening, Treatment, and end of study (EOS). Tests and procedures should be performed on schedule for all visits during Cycle 1. During all subsequent cycles, occasional changes are allowable (\pm 5 days) with permission for holidays and other administrative reasons. If extenuating circumstances prevent a patient from completing a scheduled procedure or assessment within this time, the patient may continue the study only with the permission of the Principal Investigator (PI). All EOS evaluations should occur within 30 days after the last dose of study drug, or prior to the start of subsequent anti-cancer therapy.

6.3.1 Physical Examination

A complete physical examination will be performed before dosing on Day 1 of each cycle and at the end of treatment. Vital signs (temperature, blood pressure, pulse rate, respiratory rate, weight, waist circumference) will be performed at each visit. ECOG performance status will be evaluated at day 1 of each cycle and end of study. Clinically significant AEs will be captured as well.

6.3.2 Schedule of Events

Screening/Baseline Day -21 - 0

- Informed consent and HIPAA release
- Study eligibility per inclusion/exclusion criteria
- Medical history/baseline conditions
- Physical examination
- Vital signs, including height and weight, waist circumference
- ECOG performance status
- Blood samples for hematology, comprehensive metabolic panel (fasting), lipid profile
- Serum Testosterone
- Serum PSA
- 25-OH Vitamin D
- CT scan and assessment of tumor burden, may use imaging study within 28 days of day 1
- Bone scan, may use imaging study within 28 days of day 1
- Collection of concomitant medications
- Collection of adverse events

Month 1 Day 1

COMIRB/Protocol # 14-0909**Protocol Version:****4.27.2018 PI: [name]**

- Physical examination
- Vital signs, including weight and waist circumference
- ECOG performance status
- Blood samples for CBC, Comprehensive metabolic panel (fasting), PSA, N-telopeptide, bone specific alkaline phosphatase, estradiol, hs-CRP
- Optional tubes of blood for future biomarker testing
- FACT-P, SHIM completed
- DXA scan (+/-14 Days of Day 1 Dosing); note that there must be a 14 day separation of bone scan and a DXA scan
- Short Physical Performance Battery
- Collection of concomitant medications
- Collection of adverse events
- Dosing of medication, or documentation of continued dosing
- Verification of calcium/vitamin D administration

Month 2 Day 1 +/- 5 days

- Physical examination
- Vital signs, including weight and waist circumference
- ECOG performance status
- Blood samples for CBC, Comprehensive metabolic panel (fasting), PSA, testosterone
- Collection of concomitant medications
- Collection of adverse events
- Dosing of medication, or documentation of continued dosing
- Verification of calcium/vitamin D administration

Month 4 Day 1+/- 5 days

- Physical examination
- Vital signs, including weight and waist circumference
- ECOG performance status
- Blood samples for CBC, Comprehensive metabolic panel (fasting), testosterone, PSA, N-telopeptide, bone specific alkaline phosphatase, lipid profile, estradiol, hs-CRP
- Optional tube of blood for future biomarker testing
- FACT-P, SHIM completed
- DXA scan (+/-14 Days of Day 1 Dosing); note that there must be a 14 day separation of bone scan and a DXA scan
- Short Physical Performance Battery
- Collection of concomitant medications
- Collection of adverse events
- Dosing of medication, or documentation of continued dosing
- Verification of calcium/vitamin D administration

Month 7 Day 1+/- 5 days

- Physical examination
- Vital signs, including weight and waist circumference
- ECOG performance status

COMIRB/Protocol # 14-0909**Protocol Version:****4.27.2018 PI: [name]**

- Blood samples for CBC, Comprehensive metabolic panel (fasting), testosterone, PSA, N-telopeptide, bone specific alkaline phosphatase, lipid profile, estradiol, hs-CRP, 25-OH Vitamin D
- Optional tubes of blood for future biomarker testing
- FACT-P, SHIM completed
- CT scan and assessment of tumor burden +/- 5 days
- Bone scan +/- 5 days
- Short Physical Performance Battery
- Collection of concomitant medications
- Collection of adverse events
- Dosing of medication, or documentation of continued dosing
- Verification of calcium/vitamin D administration

Month 10 Day 1+- 5 days

- Physical examination
- Vital signs, including weight and waist circumference
- ECOG performance status
- Blood samples for CBC, Comprehensive metabolic panel (fasting), testosterone, PSA, N-telopeptide, bone specific alkaline phosphatase, lipid profile, estradiol, hs-CRP
- Optional tube of blood for future biomarker testing
- FACT-P, SHIM completed
- Short Physical Performance Battery
- Collection of concomitant medications
- Collection of adverse events
- Dosing of medication, or documentation of continued dosing
- Verification of calcium/vitamin D administration

Month 13 Day 1 or End of Treatment (+/- 5 days)

- Physical examination
- Vital signs, including weight and waist circumference
- ECOG performance status
- Blood samples for CBC, Comprehensive metabolic panel (fasting), testosterone, PSA, N-telopeptide, bone specific alkaline phosphatase, lipid profile, estradiol, hs-CRP, 25-OH Vitamin D
- Optional tubes of blood for future biomarker testing
- FACT-P, SHIM completed
- DXA scan (+/- 14 Days of Day 1 Dosing); note that there must be a 14 day separation of bone scan and a DXA scan
- CT scan and assessment of tumor burden +/- 5 days
- Bone scan +/- 5 days
- Short Physical Performance Battery
- Collection of concomitant medications
- Collection of adverse events

End of Study (EOS) safety visit

- Physical examination
- Vital signs, including weight and waist circumference

- ECOG performance status
- Blood samples for CBC, Comprehensive metabolic panel
- Collection of concomitant medications
- Collection of adverse events

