Other Participating Site (enrolling subjects)	University of Colorado Health - Poudre Valley Hospital (UCH-North) Site Principal Investigator: [name]
STUDY DESIGN	
Multi-center, open label, randomized, phase II trial evaluating the incidence of metabolic syndrome within 12 months in patients treated with enzalutamide in comparison with androgen deprivation therapy for treatment of advanced prostate cancer. Enzalutamide 160mg orally daily versus standard androgen deprivation therapy. Acceptable forms of ADT will be specified and this therapy must result in castrate levels of testosterone. Patients will be treated for a 12-month period and assessed for the development of metabolic syndrome at 3 month intervals. Patients with continued clinical benefit beyond the 12-month endpoint may continue on their assigned treatment through standard of care prescribing methods.	

TABLE 1: Schedule of Events	Screening Day 0	Start of Treatment Month 1, Day1 ²	Month 2, Day1	Month 4, Day 1	Month 7, Day 1	Month 10, Day 1	Month 13, Day 1 End of Treatment	End of study ⁶
Informed Consent	X							
VISIT ASSESSMENTS								
Adverse events assessment	X	X	X	X	X	X	X	X
Review medication list	X	X	X	X	X	X	X	X
Physical Exam and history	X	X	X	X	X	X	X	X
Vital signs, including weight, waist circumference	X	X	X	X	X	X	X	X
Height	X							
Performance Status	X	X	X	X	X	X	X	X
LABORATORY STUDIES								
CBC, Comprehensive metabolic panel (fasting for glucose)	X ¹	X	X	X	X	X	X	X ⁸
PSA	X	X ⁷	X	X	X	X	X	
Lipid Profile (including triglycerides and HDL)	X			X	X	X	X	
N-Telopeptide, Bone specific alkaline phosphatase, hs-CRP, estradiol		X		X	X	X	X	
Testosterone	X		X	X	X	X	X	
25-OH Vitamin D	X				X		X	
IMAGING								
Fill out QOL questionnaires (FACT – P and SHIM)		X		X	X	X	X	
Bone densometry (DXA)		X ⁹		X				X ⁹
CT scan of chest, abdomen, pelvis ^{3, 4}	X				X		X	
Nuclear Bone scan ^{3,4}	X				X		X	
TREATMENT								
Enzalutamide dosed at 160mg po daily		X	X	X	X	X		
GNRH agonist/antagonist (Standard of care)		X	X	X	X	X		
Calcium/Vitamin D ⁵		X	X	X	X	X		
OTHER								
Short physical performance battery		X		X	X	X	X	
Optional biomarker blood testing (3 tubes, see lab manual)		X		X	X	X	X	

1 May be performed from day -14 to 0. Screening is day 0.

2 Day 1 Month 1 must occur with 21 days of screening. Visit days of the remaining months must occur +/- 5 days to date on the calendar.

3 May be performed Day - 28 - Day 0

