4. STUDY DESIGN

4.1 Overview of Study Design

This study is a multi-center, open label, randomized, phase II trial of the incidence of metabolic syndrome within 12 months in patients treated with enzalutamide in comparison with androgen deprivation therapy for treatment of advanced prostate cancer. This will include patients with biochemically recurrent disease, metastatic disease, and patients offered ADT as primary therapy if they are not candidates for local therapy. Fifty-six patients will be 1:1 randomized to one of two treatment arms with metastasis as a stratification factor. Patients will be treated for a 12-month period continuously and assessed for the development of metabolic syndrome at 3-month intervals.

Treatment will be administered for a 12-month period. Enzalutamide will be taken orally on each day of the cycle. Androgen deprivation therapy will be administered according to standard of care; however, there will be no intermittent dosing of this treatment. Acceptable forms of ADT must result in castrate levels of testosterone (<50ng/dL), and may include: leuprolide, goserelin, histerelin, triptorelin, degarelix, and surgical castration. Toxicity will be evaluated according to National Cancer Institute Common Terminology Criteria for Adverse Events (NCI CTCAE), Version 4.1 ³⁵. Metabolic syndrome will be diagnosed by assessing a patient's blood pressure, waist circumference, fasting glucose, high density lipoprotein (HDL), and triglyceride level and determined according to the Adult Treatment Panel III criteria ³⁶.

Analysis of bone turnover will include measurement of urinary N-telopeptide and serum bone-specific alkaline phosphatase. A dual-energy x-ray absorptiometry scan (DXA) will also be performed at enrollment, month 3 and EOT. This scan will provide information on bone density changes induced by treatment.

Quality of life questionnaires will be administered at each study visit. Physical function changes will be assessed via the Short Physical Performance Battery; the SPPB incorporates 3 validated portions to assess a patient's balance and mobility. Changes in systemic inflammation will be assessed via circulating hs-CRP levels. Additional collection of complete blood counts and chemistries will provide safety information. This testing will occur in the clinic setting every 3 months as well.

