9.3 Treatment Group Assignments

Patients will be assigned through the randomization process with a 1:1 ratio of patients in each treatment group. Randomization will occur centrally through a non-clinical project manager at the coordinating site. Participating sites will contact this central manager for randomization assignment during regular business hours (M-F 8-5pm).

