10.1.1 Endpoint Analysis

Primary endpoint

Metabolic syndrome incidence will be summarized by the proportion of patients with at least 3 of the 5 pre-specified criteria within the first 12 months of therapy.

Secondary endpoint

The secondary endpoints will be presented as follows:

Metabolic syndrome incidence will be summarized by the proportion of patients acquiring with at least 3 of the 5 pre-specified criteria within the first 6 months of therapy.

The change in bone turnover markers from baseline will be assessed for each treatment group. Measurements will be taken at day 1 of each cycle and reported as a continuous variable. A paired t-test will test within an arm as to whether the change from baseline to each time point is significantly different from zero.

The change in bone density, free fat mass, and fat mass will be measured at baseline, 3 months and 12 months and assessed for each treatment group. A paired t-test will test within an arm as to whether the change from baseline to each time point is significantly different from zero.

The change in QOL scores as measured by the FACT-P and SHIM at each visit, will be assessed in each treatment group.

Median time to PSA progression as defined in section 7.2. Time to PSA progression is defined as the time from randomization to the earliest objective evidence of PSA progression as defined per

protocol. If a patient has had a decline in PSA while on study, the PSA progression date is defined as the time from documented PSA nadir to an increase in PSA with confirmation as defined by protocol. Time to radiographic progression is defined as the time from randomization to the earliest objective evidence of radiographic progression as defined per protocol. Patients will be monitored at regular intervals for PSA change and radiographic change. Log rank test will be used to compare the distributions of above variables between the group treated with enzalutamide to the group on standard ADT.

The change in markers of inflammation as measured by circulating hs-CRP will be obtained at the beginning of each cycle.

Adverse events data will be summarized using tables and descriptive statistics.

The change in SPPB from baseline to 12 months will be measured as a continuous outcome. A clinically relevant change is a change in total score of 1, with a standard deviation at baseline of 1.5⁴².

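### Baseline FACT-P, SHIM and SPPB are first taken on the open-label treatment start day, and nothing requires them before the arm is disclosed

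*Combined protocol and SAP*

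**What the plan says.** Section 4.1 describes the design: "This study is a multi-center, open label, randomized, phase II trial".

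The Screening/Baseline list in 6.3.2 contains neither questionnaire and no SPPB. The Month 1 Day 1 list contains "FACT-P, SHIM completed", "Short Physical Performance Battery" and, at the same visit, "Dosing of medication, or documentation of continued dosing". In Table 1, the rows for "Fill out QOL questionnaires" and for the SPPB have their first mark under the start of treatment and none under screening.

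Section 6.2 names the randomisation tool. Section 9.3 gives the process: "Randomization will occur centrally through a non-clinical project manager at the coordinating site", with sites making contact in business hours. Neither gives a day or visit, and neither Table 1 nor 6.3.2 has a randomisation entry. Table 1 (note 2) allows up to 21 days from screening to Day 1. The only assessment that 6.3.1 ties to the time before dosing is the physical examination.

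On analysis, 10.1.1 says: "The change in QOL scores as measured by the FACT-P and SHIM at each visit, will be assessed in each treatment group". It treats SPPB change from baseline to 12 months as continuous, with a relevant change of 1 point and a baseline SD of 1.5. It then plans a one-group t-test at 0.05 for each outcome measure. Section 7.4 calls the use of FACT-P and SHIM descriptive.

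**The concern.** FACT-P and SHIM are self-reported, and staff may help with completion (7.4). The SPPB depends partly on effort and is timed by a coordinator for whom no blinding is described (7.5). If a man has just learned whether he will receive the new oral agent or standard ADT, his answers or effort may move, and the movement may differ by arm.

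That shift would sit in the reference value and so enter every later change score for these instruments. It could then be read as an effect on quality of life, sexual health or physical function. No earlier value is scheduled in Table 1 or 6.3.2, so the analysis could not remove it.

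**Working it through.** **1. What order does the plan allow?** Treatment differs by arm, so the arm must be known by the time of dosing at Month 1 Day 1. Two sequences comply with the text:

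- Forms and SPPB, then randomisation, then dosing, all on Day 1. The baseline is free of the arm.
- Randomisation at any time in the window of up to 21 days, or on Day 1 before the forms. The baseline is taken with the arm known.

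Nothing in 6.2, 6.3.1, 6.3.2, 9.3 or Table 1 excludes the second sequence.

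**2. The plan's own figure.** No power or sample size is stated for these three outcomes. The only design figure is for the primary endpoint: 28 per arm, 7% against 32%, one-sided 0.05, 80% power, actual alpha 0.054. Exact binomial enumeration of the pooled chi-square gives power 81.1% and type I error 0.0538 at the mean rate 0.195. Those figures reproduce, and this point does not depend on them.

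**3. Sensitivity of the planned within-arm test, SPPB only.**

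Inputs:
- n = 28 per arm (10.1).
- Level 0.05 (10.1.1), taken as two-sided.
- SD of change: assumed. The value 1.5 equals the stated baseline SD; 1.0 and 2.0 show the range.
- Baseline shift δ: assumed, because the documents give no value.
- No true change, and the shift is absent at 12 months.

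Formula: the test statistic follows a noncentral t with n − 1 = 27 degrees of freedom and noncentrality δ√n / SD. The critical value is 2.052, and the false-positive rate is P(|T| > 2.052).

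At SD 1.5, √28 / 1.5 = 3.528, so:
- δ = 0.1: noncentrality 0.353, rate 6.3%
- δ = 0.25: noncentrality 0.882, rate 13.6%
- δ = 0.5: noncentrality 1.764, rate 39.8%

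| SD of change | δ = 0.1 | δ = 0.25 | δ = 0.5 |
|---|---|---|---|
| 1.0 | 8% | 25% | 72% |
| 1.5 | 6% | 14% | 40% |
| 2.0 | 6% | 10% | 25% |

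With no shift, every entry is 5%.

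**4. Fewer men at 12 months.** Progression ends study treatment (4.4.2, 7.2), so not all 28 may be measured. With an assumed 20 men and SD 1.5, the rates for shifts of 0.25 and 0.5 are 10.9% and 29.4%.

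**5. Between-arm comparison.** The plan names none for these outcomes. If a t-test were run with 28 per arm, SD 1.5 and a shift in one arm only, the noncentrality is δ / (SD√(2/28)) on 54 degrees of freedom. The rates are 9% at 0.25 point and 23% at 0.5 point.

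**The case against.** The strongest objections, and what stands of each:

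- **The arm is not shown to be known.** A reader might infer that allocation is always known at these baselines. The documents do not say so, because completing the forms on Day 1 and randomising afterwards would comply. This stands: the defect is an order left open.
- **Flare cover does not settle it.** Section 4.3 allows an anti-androgen up to 14 days before medical castration, which might suggest that the arm is disclosed early. But exclusion criterion 3 tolerates short prior anti-androgen use, so such use before Day 1 does not show that the arm was known. This stands.
- **Not every change score is exposed.** A reader might extend the point to all change-from-baseline outcomes. Knowledge of the arm does not plausibly move hs-CRP, the bone turnover markers, DXA or CT measures. This stands.
- **A screening questionnaire may already be required.** Sections 4.1 and 7.4 call for the questionnaires at every study visit, and 6.3 counts screening among the visit periods. This stands only as a conflict. Table 1 and 6.3.2 omit the questionnaires at screening and also at Month 2, and the wording does not cover the SPPB.
- **The figures are assumed and concern the least susceptible instrument.** The SPPB is a timed test with set scoring, and no figure is available for FACT-P or SHIM. This stands, so the figures show sensitivity and are not an estimate.
- **A post-allocation baseline might cancel a lasting expectation effect.** Patients and staff stay unblinded. If expectation acted equally at baseline and at follow-up, it would drop out of the change score, whereas a pre-allocation baseline would leave it in. That requires the effect to stay constant for 12 months, which nothing in the documents supports. It is not a reason to prefer a baseline that may depend on the arm.

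**Conclusion.** The point holds in a limited form. As written, the plan permits the reference values for FACT-P, SHIM and SPPB to be recorded after the arm is known, and a shift at that moment could not be repaired in analysis. It does not show that this happens in every man or in any given man.

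Only these three secondary outcomes are exposed, and two of them are to be used descriptively. A descriptive change score would carry the same bias as a tested one.

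The size is unknown. The illustrative rise from 5% to about 6%, 14% or 40% rests on an assumed SPPB shift of 0.1, 0.25 or 0.5 point, an assumed SD of change of 1.5, all 28 men measured at 12 months, and a shift confined to baseline. The change is worth making because it is cheap and removes the question.

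**What to change.** - In Table 1 and 6.3.2, schedule the baseline FACT-P, SHIM and SPPB after consent and before the site contacts the central manager for the assignment. This can be in the screening period, or on Day 1 if randomisation also takes place that day.
- Define that pre-randomisation value as the baseline in 10.1.1.
- Add a randomisation entry to the schedule, and record the date and time of the assessments and of the assignment so that the order can be checked.
- Reconcile the every-visit wording in 4.1 and 7.4 with Table 1.

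**Cost.** One amendment to the schedule wording; no sample-size or power figure changes. With the screening option, the baseline may be up to 21 days older and a few screen failures complete two questionnaires and a short physical test. The Day 1 option avoids the older baseline, but it needs central randomisation within business hours and arm-specific treatment available the same day. The sponsor should confirm that this is workable before choosing it.

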7. STUDY ASSESSMENTS

7.1 Assessment of metabolic syndrome

The primary endpoint is the determination of the incidence of metabolic syndrome in patients with advanced prostate cancer treated with either enzalutamide or standard ADT. Metabolic syndrome will be assessed every 3 months and defined by the presence of 3 of the following five traits³⁶:

- Abdominal obesity, defined as a waist circumference >102 cm (>40 in)
- Serum triglycerides ≥ 150 mg/dL (1.7 mmol/L) or drug treatment for elevated triglycerides
- Serum HDL cholesterol <40 mg/dL (1 mmol/L) or drug treatment for low HDL
- Blood pressure $\geq 130/\geq 85$ mmHg or drug treatment for elevated blood pressure
- Fasting plasma glucose (FPG) ≥ 100 mg/dL (5.6 mmol/L) or drug treatment for elevated blood glucose

Patients may continue on treatment even upon development of metabolic syndrome at the discretion of the PI.

7.2 Efficacy Evaluations

7.2.1 PSA

Patients will be monitored for clinical efficacy while on study. Serum PSA will be obtained every 3 months. PSA rise is allowable at the discretion of the investigator. However, patients must discontinue treatment if there is evidence of PSA progression as defined by an increase in $\geq 50\%$ from nadir and an absolute increase of at least 2 ng/mL above the nadir, occurring at least 12 weeks after start of therapy that is confirmed by two consecutive increases taken at least 2 weeks apart. The date of first recorded increase will serve as the date of progression.

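### Sections 7.2.1 and 10.1.1 leave both the date and the time origin of PSA progression open, so the median and the log-rank result depend on which rule is applied

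*Combined protocol and SAP*

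**What the plan says.** Section 7.2.1 sets two thresholds that must both be met: a rise of at least 50% over nadir, and "an absolute increase of at least 2 ng/mL above the nadir". It adds a timing and confirmation condition: "occurring at least 12 weeks after start of therapy that is confirmed by two consecutive increases taken at least 2 weeks apart". The dating sentence follows: "The date of first recorded increase will serve as the date of progression". The same paragraph tolerates rises short of progression ("PSA rise is allowable at the discretion of the investigator") and sets the sampling ("Serum PSA will be obtained every 3 months"). Table 1 adds a sample at Month 2 Day 1.

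Section 10.1.1 first says "Time to PSA progression is defined as the time from randomization to the earliest objective evidence of PSA progression", with progression as the protocol defines it. The next sentence covers a man whose PSA has fallen during treatment: "the PSA progression date is defined as the time from documented PSA nadir to an increase in PSA with confirmation as defined by protocol". The endpoint is summarised by its median and compared between arms by log-rank test. Sections 2.2 and 3.2 list it as secondary.

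**The concern.** The conditions say which men have an event. The dating sentence says when, and it carries none of those conditions over. Sub-threshold rises are expected and recorded on treatment, so an analyst applying the sentence as written could take the first value above nadir, however small, once the man later qualifies. In a man with no PSA decline that value could be the Month 2 Day 1 sample, about one month in and before the 12-week minimum.

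The statistics section ought to resolve this but adds a second difficulty. Its first sentence points to the first qualifying value, timed from randomization. Its next sentence starts the clock at nadir, and refers the size of the increase back to the protocol definition without stating it. That second sentence is likely to cover most men, at least on enzalutamide: Section 1.5 reports that 92.5% of men in the monotherapy trial reached an 80% PSA decline.

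At stake are the median and the log-rank comparison for a named secondary endpoint in 56 men. The trial is open label, so the choice of rule should not wait until data have been seen.

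**Working it through.** **Plan's own figure.** The documents give no design figure for this endpoint. The one they do give, for the primary endpoint (28 per arm, 7% v 32%, one-sided chi-square), reproduces by exact enumeration: power 81.1% against the stated 80%, and type I error 0.0538 at the pooled rate of 19.5% against the stated 0.054. It does not depend on PSA dating.

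**Inputs from the documents.** Both thresholds and the 12-week rule come from Section 7.2.1. On-treatment PSA falls at about months 1, 3, 6, 9 and 12 (Table 1: Day 1 of Months 2, 4, 7, 10 and 13). Section 1.5 gives a median PSA fall of 99.6% on enzalutamide, so a baseline of 10, 25 or 100 ng/mL goes to 0.04, 0.1 or 0.4 (baseline × 0.004).

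**Assumptions, none in the documents.** PSA regrows exponentially from nadir; nadir falls at month 1 or month 3; doubling time is 1, 1.5, 2 or 3 months; randomization and treatment start coincide.

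**Formulas.**
- Threshold = max(1.5 × nadir, nadir + 2). Below a nadir of 4 ng/mL the 2 ng/mL condition binds.
- Doublings needed = log2(threshold / nadir).
- Back-dating = first visit meeting both thresholds minus first visit above nadir.

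**Results.** Ranges run over the doubling times for which the thresholds are reached by month 12.

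| Nadir (ng/mL) | Threshold | Fold rise (doublings) | Back-dating, nadir at month 1 | Back-dating, nadir at month 3 |
|---|---|---|---|---|
| 0.04 | 2.04 | 51 (5.7) | 6–9 months | 3–6 months |
| 0.1 | 2.1 | 21 (4.4) | 3–9 | 3–6 |
| 0.5 | 2.5 | 5 (2.3) | 3–6 | 0–6 |
| 1 | 3 | 3 (1.6) | 0–3 | 0–3 |
| 2 | 4 | 2 (1.0) | 0–3 | 0 |
| 4 | 6 | 1.5 (0.58) | 0 | 0 |

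Three limits apply to the table.
- At nadir 0.04 with a doubling time of 2 or 3 months, and at nadir 0.1 with 3 months, the thresholds are not reached by month 12. There is then no event to back-date.
- A value that first qualifies at month 12 has no later scheduled PSA to confirm it, because the End of Study visit has none. Counting only men who qualify by month 9, the largest shift is 9 − 3 = 6 months with nadir at month 1, and 9 − 6 = 3 months with nadir at month 3. The 9-month figure needs an unscheduled confirmatory sample.
- The link with nadir depth comes from the growth model. With linear growth of 0.5 ng/mL per month, crossing time is max(2, 0.5 × nadir) / 0.5: 4 months for any nadir up to 4, and 10 months at nadir 10.

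**One series, four answers.** Take nadir 0.5 at month 1 and doubling time 3 months, so PSA = 0.5 × 2^((month − 1)/3). That gives 0.79 at month 3, 1.59 at month 6, 3.17 at month 9 and 6.35 at month 12. The threshold is 2.5.

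| | From randomization | From nadir (month 1) |
|---|---|---|
| First increase of any size (month 3) | 3 months | 3 − 1 = 2 months |
| First qualifying increase (month 9) | 9 months | 9 − 1 = 8 months |

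**The case against.** The dating sentence has a sensible reading with no back-dating. The sentence before it has just described the relevant increase and required confirmation. The dating sentence may only say that the first of those increases supplies the date, and not the confirming one. Section 7.2.2 has a parallel rule: after requiring a confirmatory bone scan, it dates radiographic progression by the initial scan. The first sentence in Section 10.1.1 fits this reading too. The nadir sentence in Section 10.1.1 can also be read charitably. It defines a date as a duration, so it may be a clumsy way of saying that rises are judged against nadir, with the clock still starting at randomization.

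These points stand in part. They show that the text is ambiguous, not that it is certainly wrong. They do not remove the ambiguity: the dating sentence still states no size or timing, and the nadir sentence as written still starts the interval at nadir.

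A reader might also infer that back-dating is worst for men with deep nadirs. The documents do not support that as a general statement. It follows from assumed exponential regrowth, does not hold under linear growth, and some men with deep nadirs and slow regrowth never qualify within 12 months.

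**Conclusion.** The point holds as an unresolved definition. Read literally, Section 7.2.1 permits progression to be dated one or more scheduled visits before its own criteria are met: 0 to 9 months early under exponential regrowth, the assumed nadirs and doubling times, and the Table 1 visits. The shift is zero if the sentence means the first qualifying increase. Separately, Section 10.1.1 uses two time origins, and the second is likely to apply to most men, at least on enzalutamide. The median and the log-rank comparison therefore depend on the rule chosen.

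A reader might go further and infer that the log-rank test is biased towards one arm. That would need nadir depth or regrowth to differ between arms, and the documents give no PSA nadir figure for ADT. Neither the size nor the direction of such a bias can be computed. The primary endpoint and its power are unaffected.

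**What to change.** Use one definition in both Section 7.2.1 and Section 10.1.1, stated to apply to endpoint dating only: time to PSA progression runs from randomization to the first PSA value that meets both thresholds and the 12-week rule and is later confirmed. Delete the nadir-origin sentence from Section 10.1.1. The rule for stopping treatment is a separate matter and is left as it stands.

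The cost is a short edit in two places, made before the endpoint is analysed. No new data are needed, because the dates come from PSA values already collected under the protocol. The downside is that the reported median may be longer than under the literal reading.
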